If, based on the SMC's determination, unacceptable PK or safety criteria are met within two treatment arms, then further enrollment into the study may be stopped, and the accrual period 1 participants will be managed according to best available local TB and antiretroviral treatment. These participants will be followed off study medication for the remainder of study follow-up (up to 72 weeks).

Table 5.1. LPV/r and RBT Dose Adjustment Table

	LPV/r Dose Adjustment	Rifabutin Dose Adjustment
Arm A	No dose adjustment	
RBT PK parameters low: Adjust RBT to RBT 300 mg orally three times weekly (TIW) or 300 mg orally once daily (see section 10.4).
 
RBT PK parameters high: Decrease RBT to RBT 150 mg orally TIW
 
NOTE: The RBT <math>C_{max}</math> will be used for the purpose of individual dose adjustment for low or high RBT concentrations. A low RBT concentration will be < 250 ng/mL. A high

		RBT $C_{max}$ will be greater than 900 ng/mL.
Arm B	
 
LPV <math>C_{min}</math> < 1 mg/L and <math>C_{max}</math> < 12 mg/L: add LPV 200 mg/RTV 50 mg (one additional fixed-dose combination tablet) twice daily
 
LPV <math>C_{min}</math> < 1 mg/L and <math>C_{max}</math> > 12 mg/L: add one additional RTV 100 mg tab tablet twice daily
 
 
NOTE: A LPV <math>C_{12}</math> (or trough) will be used to define whether an individual subject's LPV/r dose is too low.
	N/A
Arm C	No dose adjustment	
RBT PK parameters low: Adjust RBT to RBT 300 mg orally TIW or 300 mg orally once daily (see section 10.4).
 
RBT PK parameters high: Decrease RBT to RBT 150 mg orally TIW
 
NOTE: See Arm A for definition of RBT low and high concentrations.

Rifabutin Dose Adjustment:

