RBT concentrations clearly associated with therapeutic success or an increased incidence of toxicity have not been established, although the range of 300-900 ng/mL for  $C_{max}$  has been associated with acceptable TB outcomes in a small number of patients. The RBT  $C_{max}$  will be used for the purpose of individual dose adjustment for low or high RBT concentrations. A low RBT  $C_{max}$  will be defined as < 250 ng/mL. This concentration represents the 25th percentile of RBT  $C_{max}$  values in 14 HIV and TB infected persons receiving a RBT dose of 150 mg once daily given in conjunction with LPV/RTV. A high RBT  $C_{max}$  will be greater than 900 ng/mL. This concentration is greater than 2 standard deviations in healthy volunteers receiving a 300 mg once daily RBT dose. The 300 mg RBT once daily dose is the usual RBT dose prior to an adjustment for the drug-drug interaction with LPV/RTV; a  $C_{max}$  > 900 ng/mL would represent an exposure above that usually seen in healthy volunteers or persons with TB.

LPV/r Dose Adjustment:

A LPV  $C_{12}$  (or trough) less than 1 mg/L will be used to define whether an individual participant's LPV/r dose is too low. A  $C_{12}$  value less than 1 mg/L is less than the 25th percentile of  $C_{12h}$  concentrations in a small study of HIV and TB infected persons receiving double dose LPV/RTV (i.e. 800/200 twice daily) with RIF, 600 mg once daily. A 12-hour post dose plasma concentration ( $C_{12h}$ ) value less than 1 mg/L is also considered the minimum threshold value for LPV by the DHHS Guidelines Panel. A  $C_{max}$  value > 12 mg/L is  $\geq$  the 75th percentile in HIV-infected persons receiving the usual twice daily 400/100 LPV/RTV dose.

NOTE: No substantive effect of RBT on LPV concentrations is expected based on prior PK data with this combination; however, if LPV levels in the ranges noted for Arm B are observed in Arm A or Arm C, then dose adjustments will be the same as for Arm B.

#### 5.1.2 For Participants Enrolled During Accrual Period 2

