#### 5.1.3 Administration

LPV 400 mg/ RTV 100 mg will be administered as two 200 mg/ 50 mg fixed-dose combination tablets orally twice daily.

LPV 800 mg/ RTV 200 mg will be administered as four 200 mg/ 50 mg fixed-dose combination tablets orally twice daily.

Additional LPV/r doses, if required as part of dose adjustments, will be administered as one 200 mg/ 50 mg fixed-dose combination tablet orally twice daily added to the original dose.

Additional RTV doses, if required as part of dose adjustments, will be administered as one 100 mg tablet orally twice daily.

RAL will be administered as one 400 mg tablet orally twice daily.

RBT 150 mg will be administered as one 150 mg capsule orally once daily, or if dose adjusted, as one 150 mg capsule orally three times weekly.

RBT 300 mg will be administered as two 150 mg capsules orally once daily, or when dose adjusted, as 300 mg (two 150 mg capsules) orally three times weekly.

All TB medications and pyridoxine obtained locally by the site will be administered as per manufacturer information or package insert.

For accrual period 1 participants in Arms A and C, it is necessary for the once daily dose of RBT to be taken with the morning dose of LPV/RTV, and for Arm C participants that the morning dose of RAL be taken with the morning dose of LPV/RTV and RBT.

In general, RBT, LPV/r, and RTV if used separately, should be taken with food; however, high fat meals should be avoided. Other anti-TB medications should be taken on an empty stomach, unless otherwise specified. Site staff should advise

the participant that if he/she does eat prior to coming to the clinic to avoid high fat meals. Specific timing of doses for PK assessments may differ from these general instructions and are indicated in section 10.0 (also see section 6.3.11).

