If the elevation of AST or ALT is thought to be due to LPV/r, anti-TB medications should be reintroduced one at a time in 3-7 day increments as described above, and if all anti-TB medications are tolerated upon re-challenge, then LPV/r should be re-introduced at the reduced dose according to Table 5.1 together with the NRTIs. If the participant was already receiving a reduced dose of LPV/r, then the re-challenge dose of LPV/r should be the dose the participant was previously receiving. If the LPV/r dose is tolerated upon re-challenge for 7 days, then the previous dose the participant was receiving, if applicable, may be restarted after discussion with the A5290 CMC. If Grade 3 or higher elevation of AST or ALT recurs with the reintroduction of LPV/r then LPV/r should be permanently discontinued, the participant should be referred to his/her primary clinician or local TB program and provided the best available ART according to local standards, and the participant should continue to be followed on study but off study-provided anti-HIV medications.

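### The re-challenge rules for LPV/r-attributed liver toxicity point to a reduced LPV/r dose that Table 5.1 does not contain

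*Protocol*

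**What the plan says.** Protocol section 7.2.1 (AST and ALT) and section 7.2.2 (bilirubin) each set out what to do once medications have been held and the abnormality has settled. Where LPV/r is the suspected cause, anti-TB drugs are brought back one at a time; if all are tolerated, "then LPV/r should be re-introduced at the reduced dose according to Table 5.1 together with the NRTIs". The sentence is identical in the two sections. Each section then adds a branch that opens "If the participant was already receiving a reduced dose of LPV/r" and sends that participant back to the dose held before.

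Table 5.1 (Protocol section 5.1.1) is the table cited. Its LPV/r column reads "No dose adjustment" for Arm A and for Arm C. For Arm B it has two entries, both conditional on a lopinavir Cmin below 1 mg/L: "add LPV 200 mg/RTV 50 mg (one additional fixed-dose combination tablet) twice daily" when Cmax is under 12 mg/L, and "add one additional RTV 100 mg tab tablet twice daily" when Cmax is over 12 mg/L. The note in the Arm B cell says that a C12 or trough value "will be used to define whether an individual subject's LPV/r dose is too low". The text below the table adds that if such lopinavir levels are seen in Arms A or C, "then dose adjustments will be the same as for Arm B".

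Section 5.1.3 (Administration) is consistent with the table: "Additional LPV/r doses, if required as part of dose adjustments, will be administered as one 200 mg/ 50 mg fixed-dose combination tablet". It also provides for added RTV tablets, and for nothing lower.

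**The concern.** A safety rule names a dose and says where to find it, and the dose is not there. This is more than missing detail: the two sections presuppose a reduced LPV/r dose, even giving a rule for people already taking one, while the table they cite only leaves LPV/r unchanged or adds to it.

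The choice of re-challenge dose has consequences inside the protocol. If the abnormality recurs on re-introduction, LPV/r is stopped. In Arms A and C, stopping LPV/r during TB treatment also requires notification of the team and a change in the RBT dose (Schema and section 5.1.1). Holds and permanent discontinuations of ARVs for toxicity make up a secondary tolerability endpoint (section 9.2.3.3.2). If sites fill the gap differently, participants with the same toxicity may be managed differently in an open-label trial.

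**Working it through.** No sample size, power or alpha figure is involved. The check is a look-up, with simple arithmetic to show the direction of each table entry.

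**1. Who reaches the pointer.** Sections 7.2.1 and 7.2.2 distinguish three attributions:
- Concomitant illness: all drugs may be resumed, with no reference to a reduced LPV/r dose.
- RBT: anti-TB drugs are re-introduced stepwise with RBT last, then the ARVs are resumed, again with no reduced LPV/r dose.
- LPV/r: once all anti-TB drugs are tolerated, LPV/r is re-introduced by way of Table 5.1.

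Only the third branch uses the faulty reference.

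**2. What the LPV/r column yields.** Starting doses are from section 5.1.1 (all twice daily, LPV/RTV in mg). The rows for Arms A and C apply the text below the table.

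| Arm | Start | Entry | Result | Direction |
|---|---|---|---|---|
| A, C | 400/100 | none | 400/100 | unchanged |
| B | 800/200 | add 200/50 | 800+200 = 1000; 200+50 = 250, so 1000/250 | up |
| B | 800/200 | add RTV 100 | 800; 200+100 = 300, so 800/300 | RTV up, LPV unchanged |
| A, C under Arm B rules | 400/100 | add 200/50 | 400+200 = 600; 100+50 = 150, so 600/150 | up |
| A, C under Arm B rules | 400/100 | add RTV 100 | 400; 100+100 = 200, so 400/200 | RTV up, LPV unchanged |

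Reduced LPV/r doses found: 0 of 3 arms.

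**3. Triggers.** The only LPV/r triggers are low-concentration triggers. The table has no row for a high lopinavir level or for toxicity.

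**4. Contrast with RBT.** The RBT column does include a decrease for Arms A and C, so the parallel RBT instructions in sections 7.2.1 and 7.2.2 reach an entry. Only the LPV/r reference fails.

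**5. Other places a reduced dose might be found.**
- Section 2.1 mentions a possible step-down dose from a small PK study in people without active TB. This is background and is not carried into Table 5.1.
- In section 5.1.1.2, Arm B moves to standard LPV/r dosing, but on completion of TB treatment, not for toxicity.
- Section 5.1.3 covers added tablets only.
- The clarification memo of 18 April 2013 deals with RIF resistance testing, medication history, FDA references and the opening of accrual. It touches neither Table 5.1 nor section 7.2.

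**6. The branch for those already on a reduced dose.** It refers to a state that no LPV/r entry in Table 5.1 can produce, so it gives no help in identifying the intended dose.

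**The case against.** The textual gap itself has no good answer, but its reach and consequences can fairly be disputed.

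- **Scope.** A reader might infer that every LPV/r re-challenge after a liver event is affected. The documents do not support that: events attributed to concomitant illness or to RBT bypass the reference. This objection stands and limits the point.
- **Site behaviour.** A reader might infer that sites will improvise, or will raise the dose by following an Arm B row. Neither is shown. The Arm B rows depend on a low lopinavir Cmin and are not toxicity rows. Section 7.0 describes its content as guidelines and makes the clinical management committee available, and the core team reviews adverse events weekly during dose-finding (section 9.5.1). These provisions make uncontrolled variation less likely, but they do not supply the dose. Committee discussion is required only before return to the previous dose, which comes after the first re-challenge.
- **Prominence of liver injury.** It would be tempting to call this the leading tolerability concern for double-dose LPV/r. Section 2.1 lists liver injury alongside gastrointestinal symptoms without ranking them, and reports that double-dose LPV/r was on the whole tolerated in the small PK study, with two asymptomatic Grade 3 or 4 transaminase elevations among 21 enrolled. Liver injury is a named concern, no more.
- **Week-48 endpoint.** A reader might infer bias in the primary comparison. No count, direction or arm imbalance can be derived. SAP section 1.6 states that accrual period 2 will not open, so the 471-participant comparison will not take place as designed. For the adverse-event criterion in SAP section 1.5.2, a related Grade 3 or 4 event within 28 days counts when it occurs, whatever re-challenge dose follows. This objection stands. What remains is tolerability: SAP section 4.2 still tabulates discontinuations within and beyond 28 days.

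**Conclusion.** This is an internal inconsistency in a safety rule, and it should be corrected. Two rules (7.2.1 and 7.2.2) direct sites to a reduced LPV/r dose in a table that has none for any of the three arms, and no other passage fills the gap. The instruction cannot be carried out as written.

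The defect is confined to Grade 3 or higher AST/ALT or Grade 4 bilirubin events attributed to LPV/r, in participants who have tolerated all anti-TB drugs on re-challenge. Their number cannot be derived. Since accrual period 2 will not open, they can come only from accrual period 1, planned at 60 participants (20 per arm) and followed to week 72. The case for correction rests on participant safety and consistent handling of tolerability, not on any demonstrated effect on the trial's conclusions.

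The verdict assumes that the LPV/r column of Table 5.1 is complete as reproduced (nothing in it suggests redaction) and that no separate study document, not available here, gives sites a reduced LPV/r dose.

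**What to change.** Issue a clarification memo that reconciles sections 7.2.1 and 7.2.2 with Table 5.1, so that the LPV/r cross-reference leads to an entry that exists in each arm. It should deal at the same time with the branch for participants already on a reduced LPV/r dose. The clinical team must decide the content; no dose or re-challenge rule is proposed here.

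The cost is memo wording. No visit, sample, endpoint or sample size changes. If LPV/r-attributed re-challenges have already taken place, a short listing by arm of the LPV/r dose used would show whether handling differed. Section 6.3.5 already requires ARV modifications to be recorded, so this needs no new data collection.

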### 7.2.2 Bilirubin

Participants entering this trial will potentially have advanced HIV disease and active TB. Elevation in bilirubin is common in this situation; however, asymptomatic or symptomatic elevation of bilirubin may also occur with RBT, RIF, or LPV/r. Because this study is designed to assess the risk/benefit ratio of second-line ART with varying doses of LPV/r and RBT as an alternative for RIF

in this population, participants with  $\leq 2.5 \times$  ULN of bilirubin will be allowed to enroll in accrual period 1 and participants with  $\leq 5 \times$  ULN of bilirubin will be allowed to enroll in accrual period 2 of the study. If the bilirubin elevation is considered most likely to be due to concomitant illness or medication, standard management, including discontinuation of the likely causative agent, should be undertaken.

For new Grade 3 bilirubin, study medications can be continued if, in the opinion of the site investigator, the possible benefits of therapy outweigh the risks.

For asymptomatic or symptomatic new elevation of bilirubin  $> 5 \times$  ULN (Grade 4), all medications must be discontinued and held until levels are Grade  $\leq 2$ , at which time therapy may be reintroduced. All medications may be restarted if the laboratory abnormalities are thought to be secondary to a concomitant illness. If the elevation of bilirubin is thought to be due to RBT, anti-TB medications should be reintroduced one at a time in 3-7 day increments, and if all other anti-TB meds are tolerated, RBT should be added last, initially at a reduced dose according to Table 5.1. If the participant was already receiving RBT at a reduced dose then the re-challenge dose should be the dose the participant was previously receiving. If the RBT dose is tolerated upon re-challenge for 7 days, then the ARVs should be restarted. If Grade 4 elevation of bilirubin recurs with the reintroduction of RBT, then RBT should be permanently discontinued and the participant should be referred to his/her primary clinician or local TB program, provided the best available anti-TB therapy according to local standards, and the participant should continue to be followed on study but off study-provided anti-TB medications.

If the elevation of bilirubin is thought to be due to LPV/r, anti-TB medications should be reintroduced one at a time in 3-7 day increments as described above, and if all anti-TB medications are tolerated upon re-challenge, then LPV/r should be re-introduced at the reduced dose according to Table 5.1 together with the NRTIs. If the participant was already receiving a reduced dose of LPV/r, then the re-challenge dose of LPV/r should be the dose the participant was previously receiving. If the LPV/r dose is tolerated upon re-challenge for 7 days, then the previous dose the participant was receiving, if applicable, may be restarted after discussion with the A5290 CMC. If Grade 4 elevation of bilirubin recurs with the reintroduction of LPV/r, then LPV/r should be discontinued, the participant should be referred to his/her primary clinician or local TB program and provided the best available ART according to local standards, and the participant should continue to be followed on study but off study-provided anti-HIV medications.

### 7.2.3 Uveitis

Uveitis presents with eye pain, redness, photophobia, blurred vision and/or decreased visual acuity. The most likely study drug to be associated with uveitis is RBT. Uveitis is reported to occur at a rate of ~3% in persons receiving RBT in doses of 450-600 mg/d. If signs or symptoms of uveitis occur in a participant assigned to a RBT regimen, RBT should be temporarily held, and the participant

should be referred to a local ophthalmologist or primary clinician for evaluation and symptomatic treatment, which may include topical (eye drops) mydriatics and/or corticosteroids. Once symptoms resolve, RBT may be restarted at a reduced dose according to Table 5.1. If the participant was already receiving a reduced dose of RBT, re-challenge with RBT at the previous reduced dose may be considered after discussion with the A5290 CMC. If uveitis recurs after re-challenge with the reduced dose, RBT should be permanently discontinued, the participant should be referred to his/her primary clinician or local TB program, and provided the best available anti-TB therapy according to local standards, and the participant should continue to be followed on study but off study-provided anti-TB medications.

#### 7.2.4 Neutropenia

Participants entering this trial will potentially have advanced HIV disease and active TB. Neutropenia is expected. Because this study is designed to assess the risk/benefit ratio of second-line ART with varying doses of LPV/r and RBT as an alternative for RIF in this population, participants with  $\geq$  Grade 2 neutropenia will be allowed to enroll in accrual period 1 and participants with  $\geq$  Grade 3 neutropenia will be allowed to enroll in accrual period 2 of the study. RBT may be associated with neutropenia. If Grade 4 neutropenia develops after study entry and RBT is considered the likely causative agent, the dose of RBT should be reduced according to recommendations in Table 5.1, and the neutrophil count should be repeated within 72 hours of the dose reduction. If the participant is already receiving a reduced dose of RBT, or if the repeat neutrophil count has not improved to Grade 3 or less, then RBT should be held, and the neutrophil count should be repeated within 72 hours. If the neutrophil count has improved to Grade 3 or less, RBT may be restarted at the reduced dose. If Grade 4 neutropenia recurs, RBT must be permanently discontinued, the participant should be referred to his/her primary clinician or local TB program, and provided the best available anti-TB therapy according to local standards, and the participant should continue to be followed on study but off study-provided anti-TB medications.

#### 7.2.5 Severe Rash/Cutaneous Reaction

Moderate to severe rash potentially related to drug hypersensitivity may occur with any of the study provided drugs, although the likeliest agents to cause rash in this setting are RIF, RBT, and RAL. It may not be possible to determine which, if any of the study drugs is the cause. Participants should be instructed to immediately stop taking RIF, RBT, RAL or other suspect drugs, and seek medical attention if they develop a rash of Grade 3 or higher, or any rash of Grade 2 or higher associated with any of the following symptoms that may be signs of a more serious reaction, such as Stevens-Johnson syndrome, toxic epidermal necrolysis, or severe hypersensitivity: fever, generalized malaise or fatigue, muscle or joint aches, blisters, oral lesions, eye inflammation, facial swelling, swelling of the eyes, lips, mouth, breathing difficulty, and/or signs and symptoms of liver abnormalities (e.g., jaundice, dark or tea colored urine, pale colored

stools/bowel movements, nausea, vomiting, loss of appetite, or right upper quadrant abdominal pain). If the rash and symptoms are thought to be due to RIF, RBT, or RAL, and no other cause can be determined, then RIF, RBT, or RAL must be permanently discontinued, the participant should be referred to his/her primary clinician or local TB program (if the suspect agent is RIF or RBT), and provided the best available anti-HIV and/or anti-TB therapy according to local standards. The participant should continue to be followed on study but off-study-provided RIF, RBT, or RAL.

#### 7.2.6 Nausea and Vomiting

Although common, nausea following initiation of therapy with ARV medications and/or TB treatment usually subsides or resolves during the first few weeks of treatment.

Steps in the management of nausea include taking the medication with food and administration of antiemetics.

#### 7.2.7 Diarrhea

Diarrhea is a common side effect of infection and medication toxicity. If no infectious cause of diarrhea is found and onset is temporally related to new medication, symptomatic management with antidiarrheal agents is appropriate.

#### 7.2.8 Recommendations for Management of Immune Reconstitution Inflammatory Syndromes

Inflammatory syndromes in participants with TB may occur shortly after the initiation of either anti-TB treatment or ART. When these syndromes are suspected, the management plan presented below should be followed. Consultation with the A5290 CMC is recommended. Note that MTB IRIS may be observed in participants who have not yet initiated or switched to second-line ART.

- Continue ART.
- Evaluate for new diagnosis of opportunistic infection or worsening of TB, as indicated.
- Continue or initiate specific therapy for the infection, if present.
- Initiate anti-inflammatory agents, initially non-steroids or, if needed, corticosteroids at the discretion of the site investigator.

